13.10 Events exempt from being reported as AE/ SAEs

13.10.1 Progression of underlying disease

In this Phase I study, which can only target a single tumour for dosing, progression is a likely outcome in patients with disseminated disease. During the follow-up period, target and control tumours in the liver will be monitored for

progression and these data will be captured on the CRF. Progression of disease by clinical means or of other tumours by radiological means will not be recorded on CRFs, however resultant death during the study period will be captured on the CRF (section 13.10.2). Adverse events including hospitalisation that are clearly consistent with disease progression will not be reported as individual AE/SAEs. Clinical symptoms of progression will only be reported as adverse events if the symptom cannot be determined as exclusively due to the progression of the underlying malignancy, or does not fit the expected pattern of progression for the disease under study. Where disease progression is so evident, in the best interests of the patient, the investigator may elect not to perform further disease assessments.

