To assess the safety of FUS-induced mild hyperthermia for drug delivery	1. Persistence of cell viability stain or percentage of cell or tissue necrosis under 30% following FUS exposure, as assessed by cytological or histological	1. Cytological or histological analysis of biopsy samples processed within 96hr of intervention†

	methods ¹⁶ ‡,§ 2. Adverse events deemed related to FUS up to 30 days post-intervention	2. Adverse event recording for 30 days post-intervention
To assess the local and systemic cytotoxic effects of ThermoDox® in this setting	1. Significant bone marrow suppression, deranged liver function and liver toxicity 2. Adverse events deemed related to ThermoDox® up to 30 days post-intervention	1. Grade 3 and 4 laboratory results from blood tests at Day 1 and Day 15 post intervention 2. Adverse event recording for 30 days post-intervention

Table 2: Secondary Objectives and Endpoints for Parts I & II of the TARDOX Study

Regarding participants for which doxorubicin has been released by optimal FUS exposure parameters:

Tertiary (Exploratory) Objectives	Tertiary (Exploratory) Endpoints	How and when data is captured
1. To establish the validity of other minimally-invasive and non-invasive methods of evaluating intratumoural uptake of doxorubicin as an alternative to that used in primary endpoint	Combined analysis of relevant end points to establish most effective alternative analytical method(s) for quantifying drug release	See below
a. Fluorescence microscopy of biopsy	Released biopsy samples exhibiting regions of nuclear or background fluorescence levels at least twice that of a suitable control, as assessed by fluorescence microscopy ‡,§	Microscopic analysis of biopsy samples processed within 96hr of intervention†
b. MR-Spectroscopy	Liver MRI/MR-Spectroscopy indicating ¹⁷ targeted delivery of doxorubicin to the tumour by demonstrating a statistically significant increase in the tumour:background ratio of signal intensity following intervention compared to baseline	MRI/MR-Spectroscopy signal within 36 hours of intervention
c. Plasma pharmacokinetics	A statistically significant decrease in total doxorubicin plasma levels over time-matched clearance levels, following HIFU-induced release	Analytical chemistry of plasma samples processed within 12hr of intervention†

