13.2 Clinical laboratory abnormalities and other abnormal assessments as AEs and SAEs

Abnormal laboratory findings (e.g., clinical chemistry, haematology, urinalysis) or other abnormal assessments (e.g., ECGs, X-rays and scans) that are judged by the investigator as clinically significant will be recorded as AEs or SAEs if they meet the definitions given above.

The investigator will exercise his or her medical and scientific judgment in deciding whether an abnormal laboratory finding or other abnormal assessment is clinically significant. By definition, **all Grade 4 laboratory abnormalities should be reported as SAEs.**

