Table 7: SAEs affecting at least 5% of patients enrolled in the Phase III, randomized, double-blinded, dummy-controlled study of the efficacy and safety of ThermoDox® in combination with RFA compared to RFA-alone in the treatment of non-resectable HCC. Data obtained from the ThermoDox® Investigator's Brochure (Amendment Version October 11, 2013).

This study involves the use of FUS to induce mild hyperthermia. A recent study performed at Oxford involving 30 patients in four trial protocols has shown *ablative* FUS or high-intensity FUS (HIFU) to be both safe and feasible for the treatment of liver and kidney tumours [45]. Adverse events are summarised in Table 8. It should be noted that thresholds of acoustic power required for mild hyperthermia, as required this study, are envisaged to be well below those required for ablative HIFU and thermal cell death.

Event	CTC grade			
	0	1	2	3
Discomfort at treatment site	6	16	7	1
Skin toxicity at treatment site	22	7	1	0
Oedema at treatment site	22	3	3	2
Fever	26	3	1	0
Other	27	3	0	0

HIFU = high-intensity focused ultrasound; CTC = common toxicity criteria. ^aNumber of patients who experienced each adverse event by grade.

Table 8: Adverse events possibly or probably related to HIFU treatment^a. Reproduced from Illing et al., 2005 [45].

Evidence for the primary endpoint for this study requires laboratory analysis of tumour tissue obtained by image guided liver biopsy through a co-axial biopsy needle as per current guidelines. The complications of performing image guided liver biopsy using guidelines have been reviewed following a recent UK-wide audit [48] and are summarised in Table 9. Out of 3496 cases, 376 patients had minor complication alone, 22 patients had at least one major complication and there were 4 deaths, all attributable to post-biopsy haemorrhage.

A: Minor Complications								
Response	Minor Pain	Severe Pain	Hypotension					
Yes	338 (9.94)	36 (1.06)	26 (0.75)					
No	3062 (90.06)	3365 (98.94)	3426 (99.25)					
Total	3400	3401	3452					
B: Major Complications								
Response	Hemorrhage	Hemobilia	Punctured Kidney	Punctured Bowel	Punctured Gallbladder	Punctured Lung	Puncture of Other Organ	Death
Yes	14 (0.40)	2 (0.06)	1 (0.03)	1 (0.03)	0 (0.00)	1 (0.03)	0 (0.00)	4 (0.11)
No	3462 (99.60)	3453 (99.94)	3457 (99.9)	3457 (99.97)	3455 (100.00)	3454 (99.97)	3471 (100.00)	3482 (99.89)
Total	3476	3455	3458	3458	3455	3455	3471	3486
C: Postbiopsy Procedure								

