13.6 Expedited reporting of SAEs

The following SAE reporting requirements apply regardless of the Investigator's assessment of the causality or expectedness of the SAE (see section 13.10 for exceptions). All SAEs should be reported on the trial SAE report form (see SAE report form and instructions for completion). Please note that the SAE report form is a paper form and these data cannot be entered into the eCRF system (OpenClinica).

SAE forms must be completed and faxed to the trial office on:

TARDOX Trial Office SAE [contact]

Or emailed (email preferred) to:

TARDOX Trial Office SAE Email: [contact]

SAE forms must be completed with all critical elements as soon as possible and submitted within 24 hours of becoming aware of the event all the vital elements being completed. If the SAE has not been reported within the specified timeframe, a reason for lateness must be provided when sending the SAE Report Form.

Investigators should also adhere to their local Trust policy for incident and SAE reporting in research.

The TARDOX trial office shall notify Celsion with a line listing report of all Serious Adverse Reactions (SARs) on a monthly basis.

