13.8 Adverse events that should be notified to trial office

AEs that are serious must be reported to trial office up to and including 30 days after the intervention date. Any SAE that occurs at any time after completion of ThermoDox® treatment or after the designated follow-up period that the investigator considers to be related to the study drug must be reported

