13.10.2 Death on study

Death due to disease under study is to be recorded on the Notification of Death CRF, and does not require reporting as a SAE, providing the death is not unexpected nor a causal relationship to the IMP or any other trial procedure suspected. Death due to all other reasons must be reported as a SAE.

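### Section 13.10.1 exempts progression-like adverse events and admissions from reporting without the suspected-causality proviso that 13.10.2 attaches to deaths

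*Protocol*

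**What the plan says.** Section 13.10.1 of the protocol lists what need not be reported when the disease progresses. For adverse events in general, admissions included, the rule is: "Adverse events including hospitalisation that are clearly consistent with disease progression will not be reported as individual AE/SAEs". The following sentence deals with clinical symptoms. They are reported "if the symptom cannot be determined as exclusively due to the progression of the underlying malignancy", or if they do not match the expected course of the disease.

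Section 13.10.2 exempts deaths from the disease under study, but only "providing the death is not unexpected nor a causal relationship to the IMP or any other trial procedure suspected".

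The other reporting rules that bear on this are:

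- Section 13.6 requires serious adverse events (SAEs) to be reported whatever the investigator's "assessment of the causality or expectedness of the SAE (see section 13.10 for exceptions". The bracket makes 13.10 an express exception.
- Section 13.8 opens with a cause-neutral rule for serious events up to 30 days after the intervention. Its second sentence adds that a later SAE "that the investigator considers to be related to the study drug must be reported".
- The opening of section 13 requires SAEs related to the drug or to a study procedure to be reported when they come to light after the monitoring period, which ends at the Day 30 visit.
- Section 13.2 treats laboratory findings and "other abnormal assessments (e.g., ECGs, X-rays and scans) that are judged by the investigator as clinically significant" as adverse events, and makes every Grade 4 laboratory abnormality an SAE.
- Section 13.3 asks for a causality opinion on drug, FUS and biopsy for each adverse event.

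**The concern.** Being consistent with progression is a weaker condition than being exclusively due to it. An event can fit progression and still have a second plausible cause. In this trial the overlap is realistic, because the organ that is heated and biopsied is also the organ that carries the tumour.

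The protocol guards against this for deaths in 13.10.2, and in part for symptoms in 13.10.1. It gives no matching safeguard for admissions or for adverse events that are not symptoms.

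What is at stake is safety capture. Section 18.2 provides no data and safety monitoring committee. The independent clinician reviews SAEs when they are received, and the Trial Management Group works from cumulative adverse event and SAE reports. An exempted event reaches neither route as an individual report, and it is missing from the adverse event summary in 17.1. Adverse events deemed related to FUS or to ThermoDox within 30 days are also secondary endpoints (section 3, Table 2).

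**Working it through.** No arithmetic applies. The check is to take each kind of event that might be mistaken for progression and ask which rule, if any, overrides the 13.10.1 exemption.

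| Event that resembles progression | Rule that keeps it reportable | Open? |
|---|---|---|
| Death with the drug or a procedure suspected | 13.10.2 proviso | No |
| Clinical symptom not solely explained by progression | 13.10.1, second test | No |
| Grade 4 laboratory abnormality | 13.2, an SAE by definition | No |
| Drug- or procedure-related SAE after the Day 30 visit | Opening of section 13 | No |
| SAE within the window, considered drug-related | 13.8, second sentence, but its rank against 13.10 is not stated | Partly |
| Admission or non-symptom adverse event within the window, FUS or biopsy suspected | 13.6 and 13.8 (first sentence) would apply, but are subject to 13.10 | Yes |
| Non-serious, non-symptom adverse event within the window, ThermoDox suspected | 13.9 would apply, but is subject to 13.10 | Yes |

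Three steps support the open rows.

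1. **Which rule prevails.** Section 13.6 gives way to 13.10 in so many words. The first sentence of 13.8 and the instruction in 13.9 to record all adverse events are general rules, and 13.10 is the specific list of exemptions from them. Nothing in 13.8 or 13.9 says that they override it. Section 13.9 is itself headed as reporting on the CRF, so an event exempt from reporting cannot safely be assumed to be recorded there.

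2. **Whether non-symptom adverse events exist.** Section 13.2 shows that they do, since clinically significant scan and laboratory findings count. A Grade 3 liver test at Day 30 is one example. It falls below the automatic Grade 4 rule, and it lies outside the laboratory endpoint, which takes "Grade 3 and 4 laboratory results from blood tests at Day 1 and Day 15 post intervention".

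3. **What the protocol intended.** Section 13.3 requires an opinion on FUS and biopsy for each adverse event. Section 13.10.2 withdraws the exemption when a procedure is suspected. The opening of section 13 says that procedure-related SAEs after the window must also be reported, which presupposes that those inside it already are. The wording of 13.10.1 therefore departs from the protocol's own intent.

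**The case against.** The best reply is that the open case nearly contradicts itself. The exemption needs a clear fit with progression, and 13.3 makes the investigator weigh drug, FUS, biopsy and malignancy as alternative causes. An investigator who suspects FUS or biopsy may well decide that the event is not clearly progression. Most admissions also begin with a symptom, and the stricter symptom test then applies. All of this stands, and it is why the gap is narrow. It does not close the gap, because the text does not say that suspicion of another cause defeats the exemption, whereas the next subsection says exactly that for deaths.

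A second reply is that data are not lost. Day 30 liver tests are scheduled for everyone (5.3), and section 19 presents all clinical data as listings. That is right for the laboratory value. It does not supply an adverse event record with a causality opinion, or a prompt report to the reviewing clinician.

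Three stronger readings are tempting, and the protocol does not support them.

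- A reader might infer from the second sentence of 13.8 that the section protects only drug-related events. Its first sentence is cause-neutral for the 30-day window. The difficulty is that 13.10 is an exception to it, not that 13.8 leaves FUS and biopsy out.
- A reader might size the gap from the liver biopsy audit in 13.4. The major complications there are haemorrhage, haemobilia, organ puncture and death. They are not shown to be events that would pass for progression, so the audit rates do not measure exempted events.
- A reader might infer that the FUS-related endpoint is materially biased. That endpoint counts events deemed related to FUS, and an investigator who deems an event related is unlikely to have set it aside as clear progression.

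**Conclusion.** The point holds as a minor one. Section 13.10.1 uses two different tests and omits the proviso of 13.10.2. As a result, an admission or a non-symptom adverse event within the window that fits liver progression, and is also suspected to come from FUS, biopsy or ThermoDox, can be exempted.

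The number of such events cannot be estimated from the protocol, and it is probably small. This is a matter of safety-reporting wording. No estimand, test, denominator or decision rule changes.

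The conclusion rests on two assumptions. The first is that 13.10 is read as an exception to the general rules in 13.8 and 13.9, as 13.6 states for itself. The second is that an event can be judged clearly consistent with progression while another cause is still suspected. If every investigator reads the word clearly as ruling out any suspected alternative, nothing is lost in practice, and the amendment only writes that reading down.

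**What to change.** Replace the two tests in 13.10.1 with one. Symptoms, other adverse events and hospitalisations are exempt only if they are exclusively due to progression of the underlying malignancy and no causal relationship to ThermoDox, FUS, biopsy or any other trial procedure is suspected. Because ThermoDox is named, the unclear ranking of 13.8 against 13.10 for drug-related events is settled too. The exemption for plain progression stays.

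The cost is a short protocol amendment and possibly a few more adverse event or SAE forms. No visits or tests are added, since adverse event review is already scheduled on Days 1, 2, 15 and 30.

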13.10.2 Death on study

Death due to disease under study is to be recorded on the Notification of Death CRF, and does not require reporting as a SAE, providing the death is not unexpected nor a causal relationship to the IMP or any other trial procedure suspected. Death due to all other reasons must be reported as a SAE.

13.10.3 Elective admissions and supportive care

Elective admissions to hospital for patient convenience or for planned procedures or investigations or treatment as specified in this protocol and standard supportive care are not SAEs, and do not require SAE reporting. Hospital admission for the following supportive care procedures are considered standard for this patient group and should not be reported as SAEs:

- Insertion of stent
- Insertion of Port-A-Cath, PICC line, etc.
- Admission for transfusion

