Primary Endpoint:	A demonstrable two-fold increase in, or value exceeding 10µg/g of, the concentration of intra-tumoural doxorubicin at the treated tumour site following FUS-induced mild hyperthermia, in at least 50% of evaluable participants.
Secondary Endpoints:	
 Part I only: Achievement of the desired range of mild hyperthermia in the target tissue as monitored by the implanted thermometry device during FUS exposure

	
 2. Persistence of cell viability stain or percentage of cell or tissue necrosis under 30% following FUS exposure, as assessed by cytological or histological methods 3. Significant bone marrow suppression, deranged liver function and liver toxicity. 4. Adverse events up to 30 days post-intervention: 
 a. Deemed related to ThermoDox® b. Deemed related to FUS
Tertiary (Exploratory) Endpoints:	
Regarding doxorubicin released by optimal FUS exposure parameters:
 
 1. Combined analysis of relevant end points to establish most effective alternative analytical method(s) for quantifying drug release: 
 a. Released biopsy samples exhibiting averaged regions of nuclear or background fluorescence levels at least twice that of a suitable control, as assessed by fluorescence microscopy b. Liver MRI/MR-Spectroscopy indicating targeted delivery of doxorubicin to the tumour by demonstrating a statistically significant increase in the tumour:background ratio of signal intensity following intervention compared to baseline c. A significant decrease of in total doxorubicin plasma levels over time-matched clearance levels, following FUS-induced release 2. Radiological evidence of tumour response at timepoints up to 60 days post-intervention in the FUS-targeted tumour and control(s), as assessed by Principles of Choi and RECIST response evaluation using MRI and CT [11, 12] and SUV_{max} using PET-CT [13]

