18.2 Data and Safety Monitoring

There is no Data and Safety Monitoring Committee (DSMC). SAEs upon receipt are reviewed by an independent nominated clinician as part of the trial office SAE Standard Operating Procedure. Cumulative reports of all AEs & SAEs are reviewed by the TMG and an Independent Trial Steering Committee (ITSC) will be in place to monitor the safety of the trial.

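### Section 13.10.3 exempts admission for transfusion from SAE reporting whatever its cause, so a transfusion admission related to the biopsy or to ThermoDox can miss expedited reporting

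*Protocol*

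**What the plan says.** Protocol section 13.10.3 first removes elective and protocol-planned admissions and standard supportive care from SAE reporting. It then adds: "Hospital admission for the following supportive care procedures are considered standard for this patient group and should not be reported as SAEs". The list has three entries: stent insertion, placement of a venous access device, and "Admission for transfusion". None is qualified by cause, timing or planning.

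Section 13.6 requires SAEs to be reported within 24 hours whatever their causality or expectedness, but refers to 13.10 for exceptions, so 13.10.3 prevails over the general rule. Section 13.1 makes in-patient hospitalisation a seriousness criterion.

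The neighbouring exemption for death from the disease under study (13.10.2) is conditional. It applies only "providing the death is not unexpected nor a causal relationship to the IMP or any other trial procedure suspected".

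On the harms concerned, section 13.4 says of the cited liver biopsy audit that "there were 4 deaths, all attributable to post-biopsy haemorrhage", and part C of Table 9 lists blood transfusion after biopsy. Section 1.3.2 gives myelosuppression as the most frequent adverse event at the trial dose (60%). A secondary endpoint is "Significant bone marrow suppression, deranged liver function and liver toxicity". Section 8.12 names transfusion among the possible treatments for doxorubicin overdose.

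**The concern.** Transfusion is a treatment for two of the harms that the trial procedures can cause: bleeding after the biopsy and marrow suppression from the drug. A participant readmitted for transfusion for either reason meets the hospitalisation criterion in 13.1, but 13.10.3 tells the site not to report the admission as an SAE, even where the investigator suspects a causal link.

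The consequence lies in the reporting route. Section 13.5 starts SUSAR assessment from the SAE form. Section 18.2 provides no data and safety monitoring committee; the prompt independent check is a nominated clinician's review of each SAE when it arrives. An event without an SAE form reaches neither. It would also be absent from the SAE count of a phase 1 study in which safety is a secondary objective and the maximum is 28 evaluable participants.

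**Working it through.** **1. Is the exemption conditional?** Set side by side:

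| Section | What is exempted or required | Condition on suspected cause |
|---|---|---|
| 13.6 | SAEs reported whatever the cause, save as 13.10 provides | gives way to 13.10 |
| 13.10.2 | death from the disease under study | lost if a link to the drug or a trial procedure is suspected |
| 13.10.3 | admission for stent, venous access device or transfusion | none |

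The word elective belongs to the heading and to the preceding sentence of 13.10.3. The sentence that introduces the list covers hospital admission without that limit.

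**2. What stays reportable despite 13.10.3?**

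- A bleed that is fatal or life-threatening, prolongs the index stay, or is medically important (13.1). Participants are observed for at least 24 hours after the intervention (Synopsis), so an early bleed would normally fall here.
- Any Grade 4 laboratory abnormality (13.2).

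What remains is a later, unplanned admission for transfusion that is related to the drug or a procedure, meets no other criterion and has no Grade 4 value. Section 8.12, which concerns overdose, places myelosuppression at about 10 to 15 days, after the usual discharge. The blood-test endpoint in Table 2 counts Grade 3 as well as Grade 4 results. A Grade 3 cytopenia is not an SAE by grade alone; hospitalisation is an obvious route to seriousness for it, and that is the route 13.10.3 closes for transfusion.

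**3. How often might this arise from biopsy?** Inputs are Table 9 (12 transfusions in 3482 cases; 14 haemorrhages in 3476) and section 16.1 (at most 28 evaluable participants).

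- The stated transfusion rate is reproduced: 12/3482 = 0.345%, given as 0.34%.
- Expected number in 28: 28 × 12/3482 = 0.10.
- P(at least one in 28) = 1 − (1 − 12/3482)^28 = 0.092, about 9%.
- For comparison, haemorrhage: 14/3476 = 0.403%; expected 28 × 14/3476 = 0.11; P(at least one) = 1 − (1 − 14/3476)^28 = 0.107.

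The calculation assumes that the audit rate applies once per participant, as one coaxial-needle procedure. The 9% is the chance of any post-biopsy transfusion. Some of those would prolong the index stay or meet another criterion, so at that rate it is an upper bound on exempted biopsy-related events. The documents do not give the share that would be exempt.

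**4. Marrow toxicity.** The documents give no rate of transfusion for marrow suppression at the trial dose, so none is computed.

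**5. Effect of one omission.** One unreported event among 28 participants is 1/28 = 3.6%. This shows how much one event weighs; it is not an estimate of how many would be missed.

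**The case against.** The strongest reply is that 13.10.3 is about routine cancer care. Its heading and first sentence speak of elective admissions and standard supportive care, and a site might not read it as covering a readmission for a procedural bleed. The other seriousness criteria and the Grade 4 rule catch most grave cases. Section 13.9 still requires every adverse event on the CRF with severity, relatedness and treatment given. The marrow endpoint is read from laboratory results and does not depend on SAE forms. Under 18.2 the trial management group reviews cumulative reports of all AEs and SAEs, and an independent steering committee monitors safety.

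Most of this stands and narrows the point. It does not remove it: the list itself carries no limit to planned or unrelated admissions, and CRF entry and cumulative review do not replace a 24-hour report or a case-by-case independent review.

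A reader might infer more than the documents support:

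- **That such events vanish from the record.** The heading of 13.10 mentions AEs as well as SAEs, but the text of 13.10.3 exempts from SAE reporting only, and 13.9 keeps the AE on the CRF.
- **That stent admissions raise the same problem.** No passage links stent insertion to the drug, the ultrasound or the biopsy.
- **That bleeding and marrow suppression are the only harms in play.** The protocol also names hypersensitivity, extravasation, liver toxicity, organ puncture and ultrasound site effects.
- **That the 18.9% neutropenia in Table 7 measures the exposure.** It is not a transfusion rate, and section 8.12 mentions transfusion for overdose only.

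**Conclusion.** The point holds in a limited form. As written, 13.10.3 overrides 13.6 for admission for transfusion regardless of cause, and lacks the causality condition that 13.10.2 has. The affected event is an unplanned, related admission for transfusion with no other seriousness criterion met and no Grade 4 laboratory value. It would be recorded as an AE but would miss the 24-hour SAE report, SUSAR assessment and the independent clinician's review, and would not enter the SAE count.

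The expected number is small. From biopsy, the chance of at least one such event in 28 participants is at most about 9%, if the audit rate applies once per participant. The contribution from marrow toxicity cannot be sized from the documents. The primary endpoint is not affected. The point deserves correction because a suspected related event could miss expedited reporting in a phase 1 trial that relies on SAE forms for prompt independent review, and because the correction is nearly free.

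**What to change.** Reconcile 13.10.3 with 13.1, 13.6 and 13.10.2 by adding one sentence: the exemption applies only if no causal relationship to the study drug or to any trial procedure (focused ultrasound, biopsy, anaesthesia) is suspected; otherwise the event is reported as an SAE. This changes reporting only and leaves patient care untouched. The cost is a protocol amendment of one sentence and, at most, a few extra SAE forms.
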